PET/MRI is likely the optimal modality to image patients for pretreatment staging of prostate carcinoma. In one study, a patient can undergo a multiparametric prostate MRI for characterization of the primary lesion and the extent of regional extraprostatic disease along with a molecular imaging study to improve the accuracy of regional staging and provide whole body staging. In addition, simultaneous acquisition of PET and MRI data allows for more accurate coregistration of MRI and PET data which may be difficult to achieve with software fusion, a key to detecting non-enlarged lymph nodes and other small lesions.

We will also develop preliminary data regarding the utility of fluciclovine-PET/MRI in early assessment of treatment response in this patient population. In men treated with radiation therapy and/or androgen deprivation therapy (ADT), early detection of treatment failure may identify patients who would benefit from additional local or intensive systemic therapy much sooner than is possible with serum PSA measurement alone. The favorable properties of PET/MRI are expected to be useful for early treatment response assessment as well. Because most of the patients in this study will not undergo

surgery, many of the post-therapy studies will be in men undergoing radiation therapy and/or androgen deprivation hormonal therapy. We will measure changes in fluciclovine uptake and MR parameters at a 3-6 month imaging time point and correlate these results with clinical follow up including progression-free survival. If fluciclovine-PET/MRI has utility for early assessment of response, men at high risk for recurrence based on imaging may be offered additional local therapy and/or systemic therapy prior to progression based on serum PSA measurements.

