2.0 Study Objectives

Specific Aim #1: Determine the concordance of imaging findings for fluciclovine-PET/MRI and mpMRI of the pelvis and prostate gland.

Hypothesis #1: Fluciclovine-PET/MRI will identify more regional lymph node metastases than mpMRI alone.

There have been numerous prior studies demonstrating the value of mpMRI for the locoregional staging for PCa. Prior studies in the setting of biochemical recurrence have demonstrated high sensitivity and specificity of fluciclovine-PET/CT for detection of recurrent disease in the prostate bed and extraprostatic disease.¹⁵ We expect the simultaneous acquisition of mpMRI and fluciclovine PET data to provide valuable preoperative staging information, with fluciclovine PET detecting metastatic disease in subcentimeter pelvic lymph nodes not identified with mpMRI alone. Additionally, fluciclovine-PET/MRI provides whole body staging in regions not evaluated by mpMRI and may detect additional distant metastases.

Specific Aim #2: Determine the correlation between organ-confined disease, lymph node metastases, extraprostatic extension, and seminal vesicle invasion on fluciclovine-PET/MRI with the expected frequencies of these metastases based on established nomograms and risk-prediction models as well as follow up fluciclovine-PET/MRI.

Hypothesis #2: Fluciclovine-PET/MRI will demonstrate metastases in the expected frequencies for patients with high-risk PCa and will regress with effective therapy.

For pretreatment patients with PCa, several clinical risk-predictors (including nomograms and Partin tables) utilize serum prostate-specific antigen (PSA), Gleason score, and clinical stage to predict organ-confined disease, the presence of extraprostatic extension, seminal vesicle invasion, and lymph node metastases.² Because majority of the high-risk prostate cancer population in this study will not undergo prostatectomy, nomograms and risk-prediction models combined with follow up fluciclovine-PET/MRI after therapy will be used as a surrogate for accuracy. If successful, this research plan will provide key data for further studies that will use histopathological confirmation as the reference standard.

Specific Aim #3: Measure changes in fluciclovine-PET/MRI at 6-12 weeks after initiation of therapy and correlate with serum PSA.

Hypothesis #3: Fluciclovine-PET/MRI parameters including fluciclovine uptake and fluciclovine-defined metabolic tumor volumes will change with effective therapy.

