3.3 Inclusion Criteria

- High-risk biopsy-proven treatment-naïve prostate adenocarcinoma (Gleason score ≥ 8 and/or serum PSA > 20)

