6.4.2 Analysis for Secondary Endpoints and Specific Aim 2: Serum prostate-specific antigen (PSA) will be measured for each patient as a clinical risk-predictor as a validated measure to identify PCa and monitor response to treatment. Patients will be identified if they have PCa metastases and response to treatment determined by PSA level (expected) and by using [¹⁸F]fluciclovine PET/MRI (observed) at baseline and 3 months after treatment. To compare observed frequencies of metastases and expected frequencies, a McNemar test will be performed at baseline and 3 month after treatment separately. Further, a generalized estimation equation (GEE) method will be used to examine the association of two diagnosis methods accounting for correlation between baseline and 3 months measurements. Sensitivity, specificity, and accuracy of using [¹⁸F]fluciclovine PET/MRI will be estimated along with 95% CI. Due to the small sample size and potential for sparse data, we may use Firth's penalized likelihood approach. Data transfer, management, and analyses will be performed using Excel and SAS v9.4.

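### Section 6.4.2 takes expected metastasis status from PSA level, not from the nomograms of Aim 2, and promises accuracy figures without a reference standard

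*Combined protocol and SAP*

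**What the plan says.** The objectives (2.0, Specific Aim #2) take the expected frequencies from nomograms and risk-prediction models. They introduce these with "For pretreatment patients with PCa, several clinical risk-predictors (including nomograms and Partin tables" and say that they "utilize serum prostate-specific antigen (PSA), Gleason score, and clinical stage to predict organ-confined disease" and the other staging features. PSA is therefore one of three inputs. The key analysis for Aim 2 in 4.6.3, the third primary endpoint in 5.1 and the secondary objective in 6.1 use the same source. Section 6.4 names a chi-squared analysis for comparing observed with expected frequencies.

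Section 6.4.2, the detailed analysis for Aim 2, does not mention nomograms. Its rule is: "Patients will be identified if they have PCa metastases and response to treatment determined by PSA level (expected". The observed side is PET/MRI. For the comparison, "a McNemar test will be performed at baseline and 3 month after treatment separately", and then "a generalized estimation equation (GEE) method will be used to examine the association of two diagnosis methods". It ends with "Sensitivity, specificity, and accuracy of using" PET/MRI, to be estimated with 95% confidence intervals. No reference is named there, and no PSA cut-off is given. One route into the study (3.3) is itself "and/or serum PSA > 20".

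Elsewhere, 1.1 and 2.0 describe nomograms combined with the follow-up scan as a surrogate for accuracy. Section 4.6.3 says that histopathology will not be obtained routinely.

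**The concern.** The analyst has two definitions of *expected* and two tests for one comparison. The definition in the detailed section is not the one in the aim. PSA level alone is a different quantity from a nomogram that also uses Gleason score and clinical stage.

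The accuracy figures are the larger risk. PSA is the only comparator in 6.4.2, so a reader is likely to take it as the reference. The figures would then measure agreement with PSA, under the name of diagnostic accuracy for metastasis. At follow-up this would count against the benefit the study hopes for. Section 1.2 expects PET/MRI to reveal treatment failure "much sooner than is possible with serum PSA measurement alone", yet a patient flagged by PET/MRI before PSA would be scored as a false positive.

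Section 6.4.2 also puts metastasis status and treatment response into one sentence. PSA is the plan's own comparator for response (Aim 3 in 2.0, and 5.3), but not for metastasis.

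**Working it through.** **1. The sections side by side.**

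| Place | Source of expected status | Test named |
|---|---|---|
| 2.0, Aim 2 | nomograms and risk models, plus follow-up PET/MRI | none |
| 4.6.3, key analysis for Aim 2 | nomograms used by the urology service | none; compare frequencies |
| 5.1 | risk models and nomograms | none |
| 6.1 | nomograms and risk models | none |
| 6.4 | not stated | chi-squared |
| 6.4.2 | PSA level | McNemar, GEE |

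**2. Could PSA in 6.4.2 be a slip for nomogram?** This does not make the section workable. McNemar needs a yes/no expected status for each patient, and a nomogram supplies a probability. The tests are planned at baseline and at 3 months, but the nomograms are described for pretreatment patients and give no expected value after treatment.

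**3. The plan's own figures (6.2).** Clopper-Pearson two-sided 95% limits with n = 15 and x = 15p (3, 3.75 and 4.5) give 4.3-48.1%, 6.9-53.4% and 9.7-58.4%. The table reproduces.

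**4. Expected counts.** With the 20-30% of 6.2, 15 × 0.20 = 3.0 and 15 × 0.30 = 4.5 node-positive patients. Both are below the usual minimum of 5 for chi-squared. With PSA as the source no count can be computed, because there is no cut-off.

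**5. The definition can decide the test (assumed extremes).** When all b discordant pairs go one way, the exact McNemar p is 2 × 0.5^b.
- Nomogram cut at 50%, every patient near 20-30%: all 15 are expected negative. With 3, 4 or 5 PET/MRI positives, p = 0.25, 0.125 or 0.0625, and sensitivity has denominator 0.
- PSA cut that makes all 15 expected positive: the same 3, 4 or 5 positives leave 12, 11 or 10 discordant pairs, so p = 0.0005, 0.001 or 0.002, and specificity has denominator 0.

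**6. PSA as reference, error-free scan.** Let π be prevalence (20-30%), and let Se and Sp be the assumed sensitivity and specificity of PSA for metastasis (60-90%; the documents give none).
- Apparent sensitivity = πSe / [πSe + (1−π)(1−Sp)]. Lowest: 0.12/(0.12+0.32) = 27%. Highest: 0.27/(0.27+0.07) = 79%.
- Apparent specificity = (1−π)Sp / [(1−π)Sp + π(1−Se)]. Lowest: 0.42/(0.42+0.12) = 78%. Highest: 0.72/(0.72+0.02) = 97%.

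**7. Effect of the entry rule.** If 5 to 10 of the 15 patients entered on PSA > 20 (assumed) and the cut-off were 20 or lower, at least 5/15 = 33% to 10/15 = 67% would be expected positive, against 20-30% from the nomograms.

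**8. Early detection at follow-up.** With m PSA-negative patients, each detection ahead of PSA lowers apparent specificity by 1/m. For an assumed m of 11 or 12 this is 9.1 or 8.3 points; for m = 15 it is 6.7.

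**9. Precision of the descriptive replacement.** With a mean nomogram probability of 25% (assumed), 3.75 positives are expected.
- The 95% range of the count is 1 to 7 of 15 for equal probabilities. It is also 1 to 7 for probabilities spread evenly over 10-40%, and for 8 patients at 5% with 7 at 48%.
- If 4 are observed, the ratio is 4/3.75 = 1.07. The Clopper-Pearson interval for 4/15 is 7.8-55.1%; divided by 0.25 it gives 0.31 to 2.20. Its coverage is 96.9%, 97.3% and 98.8% in the three cases, so it is conservative.
- For a Spearman correlation of 0.5 at n = 15, atanh(0.5) = 0.549 and SE = √(1.125/12) = 0.306, so the 95% CI is about −0.05 to 0.82.

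**The case against.** The strongest reply is that this is a 15-patient pilot described as largely exploratory, with no power calculation, and that 4.6.3 already outlines the nomogram comparison and calls for larger studies. Section 4.6.3 also has an accuracy rule of its own: the assessment closest to the nomogram frequency is taken as the most accurate. Sections 6.4 and 6.4.2 foresee sparse data and allow Yates' correction or Firth's method. These points limit the consequence, but they do not remove the conflict. The 4.6.3 rule is aggregate and cannot yield sensitivity or specificity. Yates and Firth do not say what is expected.

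It is also fair that the illustrations in steps 5 to 8 rest on assumed inputs. For example, ten patients at 5% and five at 65% also average 25%, and a 50% cut would then label 5 of 15 positive, not none. The illustrations show direction and possible size; they are not estimates.

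Two cautions about the remedy stand. The observed count depends on the positivity rule, and 6.4.1 counts any score above 0, including the low-suspicion grade. Routine-care tissue would also come from a selected group, since PET/MRI findings may prompt biopsy (3.1, 3.8.2, 4.6.3).

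**Conclusion.** The concern holds and should be fixed. Section 6.4.2 contradicts four other places on the source of expected status and differs from 6.4 on the test. Its sensitivity, specificity and accuracy have no stated reference. The surrogate described in 1.1 and 2.0 is not cited there, has no rule that turns it into a patient status, and is in part the index test repeated. This conclusion rests on the text alone. The only size that comes directly from the documents is the 3.0-4.5 expected node-positive patients; the 27-79% apparent sensitivity applies only if PSA is the reference and has the assumed accuracy.

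The stake is moderate. The comparison is a primary endpoint in 5.1 but secondary in 6.1 and in the heading of 6.4.2, and the study is descriptive. The Aim 1 trigger of more than 10% discrepancy does not depend on it.

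**What to change.** - **One definition.** In 6.4 and 6.4.2, define expected as each patient's baseline nomogram probability, and say which of the urology service's nomograms supplies it. Remove PSA-defined metastasis status and the McNemar and GEE comparisons built on it.
- **One comparison, in place of chi-squared.** For nodal disease on mpMRI, PET/MRI and the two combined, report the observed number of positive patients against the sum of the probabilities, with the Poisson-binomial 95% range of the count. A Clopper-Pearson interval divided by the mean probability may be added, labelled conservative when probabilities differ. State the score threshold for a positive patient. Treat the other staging features in the same way where the nomogram covers them.
- **Accuracy.** Drop sensitivity, specificity and accuracy, or limit them to a descriptive listing against tissue obtained in routine care, with a note that it is selectively obtained. Keep the follow-up scan as descriptive confirmation of lesions.
- **PSA.** Keep it as a nomogram input and as the comparator for treatment response. Move that analysis to a new Aim 3 subsection with a stated method, for example Spearman correlation of change in uptake and metabolic tumor volume with change in PSA, with its 95% CI and a scatterplot.
- **Rank.** State once whether the nomogram comparison is primary or secondary.

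The cost is rewording, a short subsection and one recorded probability per patient. No extra scans or patients are needed. The sponsor gives up accuracy figures that have no per-patient reference. Both replacements remain imprecise at this sample size, as step 9 of the working shows, so they can only be descriptive.

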6.5 Data and Safety Monitoring Plan

6.5.1 Pre-Study Documentation

This study will be conducted in accordance with the ethical principles that have their origin in the Declaration of Helsinki as stated in 21 CFR §312.120(c)(4); consistent with GCP and all applicable regulatory requirements.

Before initiating this trial, the Investigator will have written and dated approval from the Institutional Review Board for the protocol, written informed consent form, subject recruitment materials, and any other written information to be provided to subjects before any protocol related procedures are performed on any subjects.

The clinical investigation will not begin until either FDA has determined that the study under the Investigational Drug Application (IND) is allowed to proceed or the Investigator has received a letter from FDA stating that the study is exempt from IND requirements.

6.5.2 Institutional Review Board Approval

The protocol, the proposed informed consent form, and all forms of participant information related to the study (e.g. advertisements used to recruit participants) will be reviewed and approved by the UAB IRB. Prior to obtaining IRB approval, the protocol must be approved by the UAB Comprehensive Cancer Center Protocol Review Committee (PRC). The initial protocol and all protocol amendments must be approved by the IRB prior to implementation.

6.5.3 Informed Consent

All participants must be provided a consent form describing the study with sufficient information for each participant to make an informed decision regarding their participation. Participants must sign the IRB-approved informed consent form prior to participation in any study specific procedure. The participant must receive a copy of the signed and dated consent document. The original signed copy of the consent document must be retained in the medical record or research file.

6.5.4 Changes in the Protocol

Once the protocol has been approved by the UAB IRB, any changes to the protocol must be documented in the form of an amendment. The amendment must be signed by the Investigator and approved by the IRB prior to implementation.

If it becomes necessary to alter the protocol to eliminate an immediate hazard to patients, an amendment may be implemented prior to IRB approval. In this circumstance, however, the Investigator must then notify the IRB in writing within five (5) working days after implementation.

6.5.5 Adverse Event Reporting

As with many IV administered agents, [¹⁸F]fluciclovine could cause an allergic reaction that could potentially pose a threat to life (anaphylaxis). This has not been observed in limited human exposure to date. Reasonable precautions should be taken, consistent with normal radiologic and clinical facility practice. The patient should be monitored until the PET procedure is completed, and trained personnel and emergency equipment should be available per facility standards.

Qualifying Adverse Events (AEs), including Serious Adverse Events (SAEs), as defined herein, will be reported via the FDA Adverse Event Expedited Reporting System (AERS). For the [¹⁸F]fluciclovine IND we will report adverse events based on the FDA final rule for IND safety reporting requirements under 21 CFR part 312 published on September 29, 2010 and implemented on March 28, 2011. This investigational study is not a BA or BE study so 21 CFR part 320 is not applicable. Adverse events will also be reported to the UAB IRB according to their requirements.

Reporting of Serious Adverse Events (SAEs) to Blue Earth Diagnostics (BED): In addition to reporting of SAEs to the responsible IRB and Health Authority, the Principal Investigator or designee will document all SAEs that occur following receipt of [¹⁸F]fluciclovine (whether or not related to study drug) to BED. Such SAEs must be reported within 24 hours of Principal Investigator or designee becoming aware of the event. All SAE information must be recorded and faxed or scanned and emailed to:

Blue Earth Diagnostics SAE E mail:	[contact]
Tel:	[name] ([name])
[contact]

Additional and further requested information (follow-up or corrections to the original case) will be detailed and faxed/mailed to the same address and must include the following minimum information: The name and contact information of the reporter, the name of the study drug(s), a description of the reported SAE, with the subject identified by one or more of the following (subject initials, subject number age, sex), an investigator assessment of study drug causality, and any additional data which would aid the review and causality assessment of the case including but not limited to the date of onset, severity, the time from administration of study drug(s) to start of the event, the duration and outcome of the event, any possible etiology for the event, and the final diagnosis or syndrome, if known. If BED receives any individually identifiable health information collected or produced in the study, BED shall use and disclose only for the purpose of complying with applicable laws, provided that all such uses are disclosed in the IRB-approved informed consent form. BED will use all reasonable efforts to protect the privacy and security of individually identifiable health information and will require its business partners to do so also. BED will not contact any study subjects, unless permitted by the informed consent form.

6.5.5.1 General Definitions (from 21 CFR 312.32 (a))

Adverse Event (AE): An Adverse Event is an untoward medical occurrence associated with the use of the drug in humans, whether or not considered drug related. For this study, the drug is [¹⁸F]fluciclovine and adverse events would include any events experienced by a study participant during the Adverse Event reporting period defined in Table 1 whether or not it was considered to be related to the [¹⁸F]fluciclovine. At the conclusion of the imaging study, the imaging technologist will observe the patient and also inquire if they are back to their usual state of health. If a negative answer is received, then the physician will be called to investigate this report as a possible adverse reaction.

Adverse Reaction: An Adverse Reaction is any adverse event caused by a drug. In this study, the drug is [¹⁸F]fluciclovine.

Suspected adverse reaction means any adverse event for which there is a reasonable possibility that the IND drug caused the adverse event. For the purposes of IND safety reporting, “reasonable possibility” means there is evidence to suggest a causal relationship between the drug and the adverse event. A suspected adverse reaction implies a lesser degree of certainty about causality than adverse reaction, which means any adverse event caused by a drug.

An adverse event or suspected adverse reaction is considered “unexpected” if it is not listed in the investigator brochure or is not listed at the specificity or severity that has been observed; or, if an investigator brochure is not required or available, is not consistent with the risk information described in the general investigational plan or elsewhere in the current application.

An adverse event or suspected adverse reaction is considered “serious” if, in the view of either the investigator or sponsor, it results in any of the following outcomes: Death, a life-threatening adverse event, inpatient hospitalization or prolongation of existing hospitalization, a persistent or significant incapacity or substantial disruption of the ability to conduct normal life functions, or a congenital anomaly/birth defect. Important medical events that may not result in death, be life threatening, or require hospitalization may be considered serious when, based upon appropriate medical judgment, they may jeopardize the patient or subject and may require medical or surgical intervention to prevent one of the outcomes listed in this definition. Examples of such medical events include: allergic bronchospasm requiring intensive treatment in an emergency room or at home, blood dyscrasias or convulsions that do not result in inpatient hospitalization, or the development of drug dependency or drug abuse.

An adverse event or suspected adverse reaction is considered “life-threatening” if, in the view of either the investigator or sponsor, its occurrence places the patient or subject at immediate risk of death. It does not include an adverse event or suspected adverse reaction that, had it occurred in a more severe form, might have caused death.

Investigational Agent: An investigational agent is any agent held under an Investigational New Drug (IND) application. For purposes of this study, [¹⁸F]fluciclovine is the investigational agent.

